### 6.5.2 Secondary endpoints

- Descriptive analyses summarising change from baseline (permitting a window from -2 to 2 weeks) in Hb levels at 4 weeks (permitting a window from 3 to 5 weeks) where data are available, and 12 weeks (permitting a window from 10 to 16 weeks) after initiation of Feraccru®
- Time to normalisation of Hb levels (normalisation of Hb defined as Hb  $\geq$  12 g/dL for females and  $\geq$ 13.0 g/dL for males) after initiation of Feraccru®
- Descriptive analyses summarising change from baseline (permitting a window from -2 to 2 weeks) in ferritin levels at 4 weeks (permitting a window from 3 to 5 weeks) where data are available, and 12 weeks (permitting a window from 10 to 16 weeks) after initiation of Feraccru®
- Percentage of patients with normalised ferritin levels at 12 weeks (permitting a window from 10 to 16 weeks) after initiation of Feraccru®. Normalised serum ferritin is defined as serum ferritin concentration  $\geq$ 30 microgram/L and  $\leq$ 300 microgram/L
- Time to correction of serum ferritin levels after initiation of Feraccru®
- Descriptive analyses summarising change from baseline (permitting a window from -2 to 2 weeks) in transferrin saturation at 4 weeks (permitting a window from 3 to 5 weeks) where data are available, and 12 weeks (permitting a window from 10 to 16 weeks) after initiation of Feraccru®
- Percentage of patients with normalised transferrin saturation at 12 weeks (permitting a window from 10 to 16 weeks) after initiation of Feraccru®. Normalised transferrin saturation is defined as transferrin saturation between 20% and 50%

- Time to correction of transferrin saturation after initiation of Feraccru®
- Patient characteristics: age, sex and type of IBD
- Descriptive analyses of haematology and biochemistry parameters at baseline
- Time from diagnosis of IBD to initiation of Feraccru®
- Time from diagnosis of IDA to initiation of Feraccru®
- Descriptive analyses of prior IV iron treatment, to include at least the percentage of patients with one or more prior infusions
- Reason(s) for discontinuing each prior oral ferrous product
- Reason(s) for initiating Feraccru®
- Percentage of patients who discontinue Feraccru®
- Reason(s) for discontinuing Feraccru®
- Type, severity and time of adverse events that are related to and caused by (in the clinician's opinion) Feraccru®, from initiation of Feraccru®

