## **List of definitions**

Baseline is defined as the date of initiation of Feraccru®.

Iron deficiency anaemia is defined by the World Health Organization (WHO) as <12.0 g/dL in women and <13.0 g/dL in men.

Mild to moderate iron deficiency anaemia (secondary to either CD or UC) is also defined in this study as serum ferritin concentration <30 microgram/L or transferrin saturation of <20%.

Normalised haemoglobin (Hb) is defined in this study as Hb  $\geq$ 12.0 g/dL for females and  $\geq$ 13.0 g/dL for males.

Normalised serum ferritin is defined in this study as serum ferritin concentration  $\geq$ 30 microgram/L and  $\leq$ 300 microgram/L.

Normalised transferrin saturation is defined in this study as transferrin saturation between 20% and 50%.

Observation period is defined as 12 weeks after initiation of Feraccru® (permitting a window from 10 to 16 weeks).

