	
to clinic for routine follow-up visits.
 
 
Prospective recruitment - Patients initiated on Feraccru® during the study period will be identified and asked to provide consent at the time of Feraccru® initiation.
 

Data source(s)	Data will be collected from hospital medical records, by a member of the care team or a researcher in the study centre.
Number of centres	Five secondary care centres in the UK.
Number of subjects	Approximately 100 patients with IBD (Crohn's disease [CD] or ulcerative colitis [UC]) who are also diagnosed with IDA.
Study time period	12 weeks (permitting a window from 10 to 16 weeks to allow for routine follow up clinic visits to occur).
Patient selection	
Inclusion criteria
 
 
Male and female patients aged <math>\geq 18</math> years at the time of initiation
 
Patient presenting with mild to moderate IDA that is secondary to either CD or UC defined as: 
 
Hb <math><12.0</math> g/dL in females
 
Hb <math><13.0</math> g/dL in males
 
Serum ferritin concentration <math><30</math> microgram/L or transferrin saturation of <math><20\%</math>
 
 
 
Patient receiving Feraccru® since the time of UK launch in June 2016
 
 
Exclusion criteria
 
 
Patient receiving Feraccru® as part of an interventional clinical trial
 
Patients with severely active IBD or requiring corticosteroids at the time of initiation on Feraccru®
 
Patient with an IBD flare, as determined by the clinician
 
Patient with medical records that are not available for review
 
Patient not willing or unable to consent to study participation, or patient is deceased at the start of data collection period
 

Study endpoints	
Primary endpoint:
 
 
Percentage of patients with normalised Hb levels at 12 weeks (permitting a window from 10 to 16 weeks) after initiation of Feraccru®
 
 
Secondary endpoints:
 
 
Descriptive analyses summarising change from baseline
 

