#### 4.3 Secondary objectives

- To describe the clinical outcomes associated with the use of Feraccru® in the real world, including:
  - Change in Hb levels at 4 and 12 weeks after initiation of Feraccru®
  - Time to normalisation of Hb levels after initiation of Feraccru®
  - Change in serum ferritin levels at 4 and 12 weeks after initiation of Feraccru®
  - Percentage of patients with normalised ferritin levels at 12 weeks after initiation of Feraccru®
  - Time to correction of serum ferritin levels after initiation of Feraccru®
  - Change in transferrin saturation at 4 and 12 weeks after initiation of Feraccru®
  - Percentage of patients with normalised transferrin saturation at 12 weeks after initiation of Feraccru®
  - Time to correction of transferrin saturation after initiation of Feraccru®
- To describe the characteristics of patients receiving Feraccru® in the real world, including:
  - Age and sex
  - Type of IBD
  - Haematology and biochemistry parameters at baseline
  - Time from diagnosis of IBD to initiation of Feraccru®
  - Time from diagnosis of IDA to initiation of Feraccru®
  - Iron treatment history
  - Reason(s) for discontinuing each prior oral ferrous product
  - Reason(s) for initiating Feraccru®
  - Percentage of patients who discontinue Feraccru®
  - Reason(s) for discontinuing Feraccru®

- Type, severity and time of adverse events that are related to and caused by (in the clinician's opinion) Feraccru®, from initiation of Feraccru®

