### **6.2.1 Inclusion criteria**

- Male and female patients aged  $\geq$  18 years at the time of initiation
- Patients presenting with mild to moderate IDA that is secondary to either CD or UC, defined as:
  - Hb  $<12.0$  g/dL in females
  - Hb  $<13.0$  g/dL in males
  - Serum ferritin concentration  $<30$  microgram/L or transferrin saturation of  $<20\%$
- Patients receiving Feraccru® since the time of UK launch in June 2016

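### The week-12 ferritin and transferrin saturation percentages, and the two time-to-correction endpoints, do not separate patients low on that marker at baseline from patients who were not

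*Combined protocol and SAP*

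**What the plan says.** **Entry.** Section 6.2.1 introduces the anaemia criterion with "Patients presenting with mild to moderate IDA that is secondary to either CD or UC, defined as", and the synopsis does the same with "Patient presenting with mild to moderate IDA that is secondary to either CD or UC defined as". Each then lists the sex-specific Hb limits and one line for the iron markers. The List of definitions shows that the iron line is an either/or: the condition "is also defined in this study as serum ferritin concentration <30 microgram/L or transferrin saturation of <20" per cent. One low marker is enough.

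**Week-12 percentages.** Section 4.3 sets the objective "Percentage of patients with normalised ferritin levels at 12 weeks after initiation of Feraccru", and Section 6.5.2 repeats it with the visit window: "Percentage of patients with normalised ferritin levels at 12 weeks (permitting a window from 10 to 16 weeks) after initiation of Feraccru". Normalised ferritin is 30 to 300 microgram/L. For saturation, "Normalised transferrin saturation is defined as transferrin saturation between 20% and 50" per cent. Neither definition refers to the patient's starting value.

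**Time endpoints.** Section 6.5.2 also lists "Time to correction of serum ferritin levels after initiation of Feraccru" and "Time to correction of transferrin saturation after initiation of Feraccru", with no starting condition for either.

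**Analysis rules.** Section 9 gives general descriptive statistics and names no analysis population, at-risk set or time-to-event method. Section 9.1 restricts each analysis to patients with data and asks for the number included. Nothing in the document limits these four endpoints to patients who were low on the marker concerned at baseline.

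**The concern.** A patient who qualifies on saturation alone may start with ferritin already between 30 and 300 microgram/L. If ferritin is still there at week 12, the patient counts as normalised although there was nothing on that marker to correct. The same holds the other way round.

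The objectives present these endpoints as clinical outcomes of treatment, and Section 3.1 asks whether biochemical results from trials can be replicated in practice. A reader will therefore tend to take a *normalised* percentage as a correction rate. It exceeds that rate if patients in range at baseline are in range at week 12 more often than low patients are corrected.

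For time to correction, the plan does not say whether a patient in range at initiation has an event at time zero, is left out, or has no defined time. Two analysts could report different medians from the same data.

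The planned baseline and change summaries would probably show how many patients started in range. Because they are marginal, they cannot show how many of those patients make up the week-12 count.

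**Working it through.** **1. The plan's own figure.** Section 8 gives precision for the primary Hb percentage only. With p = 0.66 and a 95% Wald interval (the confidence level is not stated, but 95% reproduces the table), n = 1.96² × 0.66 × 0.34 / d². This gives 106.4, rounded up to 107, at d = 9 points, and 86.2, rounded up to 87, at d = 10 points. Both agree with Table 2, as do its other four rows. At n = 100 the half-width is 1.96 × √(0.66 × 0.34 / 100) = 9.3 points, consistent with the stated 9–10%. The plan gives no corresponding figure for ferritin or saturation.

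**2. What the all-patient percentage measures.** For one marker, ignoring for simplicity patients above the upper limit at baseline, let:
- f = share in range at baseline;
- s = share of those patients in range at week 12;
- c = share of baseline-low patients in range at week 12 (the correction rate).

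Reported percentage = (1 − f)c + fs, so the excess over the correction rate is f(s − c).

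**3. Numbers.** The documents give none of f, s or c, so every value here is an assumption. With s = 70–90% and c = 40–60%, s − c runs from 10 to 50 points.

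| f | Smallest excess (s = 70%, c = 60%) | Largest excess (s = 90%, c = 40%) |
|---|---|---|
| 10% | +1 point | +5 points |
| 30% | +3 points | +15 points |
| 50% | +5 points | +25 points |

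For example, take 100 patients with f = 30%, s = 90% and c = 40%. Of the 30 in range at baseline, 27 are in range at week 12; of the 70 low patients, 28 are. The reported figure is 55%, against a correction rate of 40%.

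The result depends on the grid, in which s always exceeds c:
- With c = 30%, s = 90–100% and f = 10–40%, the excess runs from 0.1 × 60 = 6 to 0.4 × 70 = 28 points.
- With s = c it is zero.
- With s = 50%, c = 60% and f = 30% it is 0.3 × (−10) = −3 points, an understatement.

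**4. The two markers together.** Every eligible patient is low on at least one marker. If the baseline values are the qualifying values, the two in-range shares therefore sum to at most 100%. With the same s and c for both markers, and the same patients measured at week 12, the two excesses sum to at most s − c. Large excesses on both at once are unlikely.

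**5. Hb.** Entry requires Hb below the same limits that define normalised Hb, so the Hb endpoints do not share the problem, provided the baseline Hb is the qualifying low value. The proviso is needed because Section 6.2.1 gives no test window, while baseline may be up to two weeks either side of initiation.

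**6. Precision after restriction.** The 95% half-width at an assumed 40% is 1.96 × √(0.24 / n): 9.6 points at n = 100, 11.5 at n = 70 and 13.6 at n = 50. If 20% lack a baseline value (assumption), n = 70 and 50 become 56 and 40, with half-widths of 12.8 and 15.2. If a further 20% lack a week-12 value (assumption), n is about 45 and 32, with half-widths of about 14.3 and 17.0.

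**The case against.** The strongest reply is that the study is descriptive, tests no hypothesis and promises no correction rate. The objective is the percentage in a stated range at 12 weeks, and the endpoint delivers exactly that. This stands: the percentages are not wrong, and the all-patient figure should stay. It does not remove the gap, because in a descriptive study the denominator decides what the description means.

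A second reply is that *correction* in plain language presupposes a low start, so an analyst could restrict the set without being told, and could take the threshold from the List of definitions. The synopsis bullet for time to Hb normalisation also states no threshold. This too has force. The missing threshold alone is only missing detail; the point is the unstated at-risk set.

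Third, the size rests wholly on assumed inputs, chosen so that s exceeds c. That is correct, and the figures illustrate the mechanism without estimating its effect.

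A reader might also infer that the counted patients were never iron deficient on that marker. The documents do not support this. Prior intravenous and oral iron history is collected (Section 6.5.3), so a patient may have been low earlier and been repleted. The accurate description is *not low at baseline*.

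**Conclusion.** The point holds for four secondary endpoints: the week-12 percentages and the times to correction for ferritin and saturation. Followed literally, the plan mixes patients not low on a marker at baseline with patients who were corrected, and no other section resolves this. That conclusion rests on the wording and is firm.

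The size is unknown. It is f(s − c), for example 3 to 15 points at f = 30% under the assumed ranges, and there is no overstatement if s is no larger than c.

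Two stronger inferences are not supported. One is that the percentages must overstate correction: that depends on s exceeding c, on which the documents give no data. The other is that the primary endpoint is compromised: low Hb is an entry requirement, so it is not affected in this way as long as the baseline Hb is the qualifying value. The sample size is also untouched. This is a cheap improvement that should be made before analysis.

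**What to change.** Amend Section 6.5.2, with matching text in Section 4.3 and the synopsis:

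1. Keep the all-patient percentage for each marker, labelled *in range at week 12*.
2. For each marker, add the percentage normalised among patients low on that marker at baseline (ferritin <30 microgram/L; saturation <20%), with n stated.
3. Limit each time-to-correction endpoint to the same baseline-low set, and define correction as the first value in the normalised range given in the List of definitions.
4. Add one shift table per marker, baseline by week 12, with categories low, in range, high and not known. Patients without a baseline value are classed as not known: they stay in the all-patient percentage but are left out of the at-risk set.

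The cost is two extra rows, two tables and one at-risk sentence. Section 6.5.3 already collects dated ferritin and saturation results from baseline to week 12, so no new data or tests are needed. The added percentages are less precise than the all-patient figures, as shown in the working, and more so where baseline or week-12 values are missing. The all-patient figures lose nothing.

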### **6.5.3 Variables to be collected**

The following study variables will be collected during the observation period to measure the study endpoints, in order to describe the use of Feraccru® in the real world.

#### **Patient demographics and other characteristics:**

- Age at initiation of treatment with Feraccru®
- Sex (Male/Female)
- Date diagnosed with IBD
- Type of IBD (CD/UC)
- Date diagnosed with IDA
- Description of IV iron treatment history, to include at least the number of prior infusions
- Description of oral iron treatment history, where available in secondary care notes

- Experience of oral ferrous products (OFPs) (Yes/No), if yes:
- Name(s) of OFP(s)
- Reason(s) for discontinuing OFP(s)

**Feraccru® treatment:**

- Date initiated on Feraccru®
- Reason(s) for initiating Feraccru®
- Date discontinued Feraccru®
- Reason (s) for discontinuation of Feraccru®

**Haematology and biochemistry parameters:**

The date(s) and result(s) of haemoglobin (Hb), ferritin and transferrin saturation will be collected from baseline (permitting a window from -2 to 2 weeks) to 12 weeks (permitting a window from 10 to 16 weeks). The date(s) and result(s) of the following haematology and biochemistry parameters will be collected at baseline only (permitting a window from -2 to 2 weeks):

- Folate
- B12
- Mean corpuscular volume
- Mean corpuscular Hb
- Platelets
- C-reactive protein (CRP)

**Adverse events:**

The details of adverse events (AEs) that are considered to be related to Feraccru® treatment, determined by clinical opinion, will be collected:

- Type, severity, start and end dates of AE/serious adverse event (SAE) with a temporal relationship to and caused by Feraccru®, as determined by the clinician

## **7. Data management and quality control**

Data collection will be completed by trained staff employed by the NHS Trust or staff from pH Associates. All data collectors will be provided with Data Collection Guidelines to provide further information regarding the completion of the electronic Data Collection Form (eDCF). The same data collector will be used at each centre, wherever possible, to ensure consistency in data collection, if feasible. All data collected will be submitted regularly in anonymised-coded form to pH Associates for data entry, cleaning and analysis.

### **7.1 Database management**

The eDCF will be developed from a paper draft and then converted to electronic form in MACRO, which is a web-based secure electronic data capture and data management tool. MACRO is compliant with FDA 21 CFR part 11 and Good Clinical Practice (GCP) and has been widely used in the UK NHS for complex interventional clinical trials and used by pH Associates on a range of real world evidence studies. A data analysis tool will be developed using Microsoft capabilities (Access®, Excel®).

### **7.2 Data quality checks**

As this study will use both retrospective and prospective methods of data collection, the quality of the study dataset will depend on the accuracy and completeness of data recorded in patients' medical records. Where data on study variables are not available, fields will be marked as 'not known' rather than left empty. Quantitative data collected for laboratory (haematology and biochemistry) parameters will be standardised per centre using laboratory reference ranges entered on the eDCF. This will allow pooling of these study parameters across centres.

All data submitted will be checked for accuracy and completeness. Queries will be raised by the pH Associates data management team. Study centres will be required to co-operate with the data management team in the resolution of these queries. On completion of the first three eDCFs from at least two centres, a pilot data review will be completed. This pilot will ensure that the study dataset can be captured feasibly and efficiently on the eDCF and the methodology for data collection is suitably robust.

In order to confirm the accuracy and quality of the data, source data verification (SDV) will be completed for a randomly selected 10% of all patients. 100% of the data collected for these patients will be reviewed by pH Associates staff. Where data collection is completed by pH Associates staff, the staff member who carries out the SDV will be different to the person responsible for data collection at that specific centre.

## **8. Study sample size**

Given the descriptive nature of this study, a preliminary estimation of the required sample size is expressed in terms of precision and not statistical power. In the literature, the percentage of patients treated with Feracceu® with reported normalised Hb at 12 weeks is approximately 66%. However, the accuracy of such estimates will vary according to the number of participants in the study. Using 66% as the percentage of patients expected to show a normalised Hb at 12 weeks, the precision of such estimates can be calculated using a Binomial confidence interval (Table 2).

**Table 2 Precision calculated using a Binomial confidence interval (Wald interval, normal approximation)**

Patients with normalised Hb at 12 weeks (%)	Precision (%)	Study patients (N)
66%	7%	176
66%	8%	135
66%	9%	107
66%	10%	87
66%	11%	72
66%	12%	60

With a sample size of 100 patients, the precision of the estimates is calculated as between 9–10%. This means that the percentage of patients treated with Feraccru® with a reported normalised Hb at 12 weeks in the study will be within 9–10% of the true population percentage.

## **9. Statistical analysis**

Analyses will be performed by pH Associates. The planned analysis will be descriptive in nature. Both distributions and descriptive statistics of central tendency (arithmetic means and medians) and dispersion (standard deviation, interquartile range) will be presented for quantitative variables. Nominal variables will be described with frequencies, percentages and modes, while ordinal variables will also have medians and interquartile ranges described. Confidence intervals will be provided for means of quantitative variables.

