	
(permitting a window from -2 to 2 weeks) in Hb levels at 4 weeks (permitting a window from 3 to 5 weeks) where data are available, and 12 weeks (permitting a window from 10 to 16 weeks) after initiation of Feraccru®
 
 
• Time to normalisation of Hb levels after initiation of Feraccru®
 
• Descriptive analyses summarising change from baseline (permitting a window from -2 to 2 weeks) in ferritin levels at 4 weeks (permitting a window from 3 to 5 weeks) where data are available, and 12 weeks (permitting a window from 10 to 16 weeks) after initiation of Feraccru®
 
• Percentage patients with normalised ferritin levels at 12 weeks (permitting a window from 10 to 16 weeks) after initiation of Feraccru®
 
• Time to correction of serum ferritin levels after initiation of Feraccru®
 
• Descriptive analyses summarising change from baseline (permitting a window from -2 to 2 weeks) in transferrin saturation at 4 weeks (permitting a window from 3 to 5 weeks) where data are available, and 12 weeks (permitting a window from 10 to 16 weeks) after initiation of Feraccru®
 
• Percentage of patients with normalised transferrin saturation at 12 weeks (permitting a window from 10 to 16 weeks) after initiation of Feraccru®. Normalised transferrin saturation is defined as transferrin saturation between 20% and 50%
 
• Time to correction of transferrin saturation after initiation of Feraccru®
 
• Patient characteristics: age, sex and type of IBD
 
• Descriptive analyses of haematology and biochemistry parameters at baseline
 
• Time from diagnosis of IBD to initiation of Feraccru®
 
• Time from diagnosis of IDA to initiation of Feraccru®
 
• Descriptive analyses of prior IV iron treatment, to include at least the percentage of patients with one or more prior infusions
 
• Reason(s) for discontinuing each prior oral ferrous product
 
• Reason(s) for initiating Feraccru®
 
• Percentage of patients who discontinue Feraccru®
 
• Reason(s) for discontinuing Feraccru®
 
• Type, severity and time of adverse events that are related to and caused by (in the clinician's opinion) Feraccru®, from initiation of Feraccru®
 

--	---

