### **9.1 Missing data**

Whilst study centres will be selected to include those expected to have the most complete data, this study involves the retrospective collection of data from medical records. As such,

it is possible that some data points will be missing. Where data are missing from the original medical record, the affected analyses will be conducted using only the results of those patients with data available (complete case analysis) and the number of patients included in each analysis will be stated. The percentage of data missing will be reported for each study variable. Missing data in itself will be of interest and should provide insight into the way patients are being managed in the UK outside the methodological constraints of a clinical trial.

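### Section 9 gives no censoring rule, estimator or risk set for the three time-to-normalisation endpoints, so the planned mean and SD can cover only patients who normalise

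*Combined protocol and SAP*

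**What the plan says.** All references are to the combined protocol and SAP.

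- **Endpoints.** Three secondary endpoints are times to an event: "Time to normalisation of Hb levels after initiation of Feraccru" (Section 1), "Time to correction of serum ferritin levels after initiation of Feraccru" (Section 6.5.2) and "Time to correction of transferrin saturation after initiation of Feraccru" (Section 4.3). All three appear in each of those sections.
- **Method.** Section 9 says: "Both distributions and descriptive statistics of central tendency (arithmetic means and medians) and dispersion (standard deviation, interquartile range) will be presented for quantitative variables". It adds confidence intervals for means. It names no time-to-event method.
- **Missing data.** Section 9.1 says: "Where data are missing from the original medical record, the affected analyses will be conducted using only the results of those patients" who have data. The number of patients in each analysis is to be stated.
- **Follow-up and tests.** Section 6.1 ends follow-up at 12 weeks, with 10 to 16 weeks allowed. Section 6.2.3 adds no tests to routine care. Section 6.5.3 collects dates and results of Hb, ferritin and transferrin saturation from baseline to week 12, and "Date discontinued Feraccru".
- **Entry and event ranges.** The list of definitions and Section 6.2.1 accept ferritin below 30 microgram/L or transferrin saturation below 20%. The list of definitions also gives the normalised range for each parameter.
- **Expected response.** Section 8 takes 66% with normalised Hb at 12 weeks.

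**The concern.** A patient whose last test is still not normal has a right-censored time: it exceeds the date of that test, but its value is unknown. A mean or SD cannot use such a patient. Following Section 9 as written therefore gives a mean and SD for normalisers only, although the endpoint reads as a property of everyone treated.

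Section 9.1 does not cure this, because a recorded low value is not missing from the record. The plan also leaves open what happens when follow-up ends anywhere from week 10 to 16, or when Feraccru® is stopped before normalisation.

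The risk set is a separate gap. Because entry needs low ferritin or low transferrin saturation, a patient can start in range on one of the two. The plan does not say whether that patient counts as time zero or is left out.

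At stake is how fast the product appears to work. A parameter that fewer than half of patients correct would still get a finite mean and median if only correctors were summarised.

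**Working it through.** **1. The plan's own figures.** The documents give no figure for the time-to endpoints. The 66% used below is the input to Table 2, which reproduces. The confidence level is not stated, so 95% two-sided is assumed. From n = 1.96² × 0.66 × 0.34 / d², d = 9% gives 106.42, rounded up to 107, and d = 10% gives 86.2, rounded up to 87. At N = 100 the half-width is 1.96 × √(0.66 × 0.34 / 100) = 9.28%, within the stated 9–10%.

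**2. Patients without a time value (Hb).** 100 × (1 − 0.66) = 34. The number is lower if some patients normalise earlier and relapse by week 12. It is higher if response is lower or tests are absent.

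**3. Direction.** Kaplan-Meier passes the weight of each censored patient to later events. Later events therefore carry at least as much weight as earlier ones, and the total is at most 1. The estimated proportion with an event by any time t cannot exceed the equal-weight proportion among normalisers. On the same test dates, the normalisers-only summary is earlier or equal, whatever the curve.

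**4. Size under frequent testing (assumed).** Assume a constant rate with 66% normalised by week 12.
- λ = −ln(0.34)/12 = 0.0899 per week.
- All-patient median = ln 2/λ = 7.71 weeks.
- Normalisers-only median, follow-up to week 12: −ln(1 − 0.66/2)/λ = 4.45 weeks.
- Normalisers-only mean, same follow-up: 1/λ − 12 × 0.34/0.66 = 4.94 weeks.
- Follow-up to week 16: the proportion normalised is 1 − exp(−16λ) = 0.763, and the normalisers-only median is 5.34 weeks.

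**5. Size under sparser testing (same curve; schedules assumed).**
- *Tests exactly at weeks 4 and 12.* The proportion normal at week 4 is 1 − exp(−4λ) = 0.302. Among normalisers 0.302/0.66 = 0.458 is below one half, so the median at these proportions is 12 with or without non-normalisers. The normaliser mean is (4 × 0.302 + 12 × 0.358)/0.66 = 8.34. With non-normalisers counted at week 12 it is 4 × 0.302 + 12 × 0.698 = 9.58, a gap of 1.24 weeks. The gap is 0.62 if half have a week-4 test and 0 if none do.
- *Tests at weeks 4, 8 and 12* (simulated, averages of the sample median): normalisers only 7.0, Kaplan-Meier 9.4, interval-censored 7.9.
- *One test uniform over weeks 10–16, plus one over weeks 3–5 in 0%, 50% or 100% of patients* (simulated, N = 100):

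| Week-4 test | Normalisers-only median | Kaplan-Meier median, test dates | Gap |
|---|---|---|---|
| 0% | 13.18 | 13.88 | 0.70 |
| 50% | 12.39 | 13.52 | 1.13 |
| 100% | 10.05 | 12.92 | 2.87 |

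**6. Sensitivity.** The range of 0 to about 3 weeks belongs to a constant rate and 66% by week 12. Under frequent testing to week 12, 50% normalised gives 12.0 against 5.0 weeks, and 70% gives 6.9 against 4.3. With tests at weeks 4, 8 and 12 and Weibull shapes 0.7, 1.5 and 2, the gap between Kaplan-Meier and normalisers-only is 4.2, 3.4 and 3.6 weeks. With tests only at weeks 4 and 12, and 40% rather than 30% normal at week 4, the normaliser median falls to 4 while the all-patient median stays at 12.

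**7. Which estimator.** In the table's scenario the true week-12 proportion is 66%. Kaplan-Meier on test dates gives 23%, 32% and 42%, because events are dated at the test that finds them. An interval-censored (Turnbull) estimate gives 65% in all three, with 95% of runs at about 50–78%.

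**The case against.** **The plan does not say that non-normalisers are dropped.** This is right. A reader might infer it from the complete-case rule, but that rule concerns data missing from the record. Restriction to normalisers is what the mean and SD force, not a stated decision.

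**The median need not be restricted.** Also right. A reader might infer that any planned median describes normalisers only. An all-patient median exists if at least half normalise and the rest are ranked last, and Section 9 also promises distributions. The plan gives no such ranking rule, so it would have to be chosen later.

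**Larger figures are tempting.** With half tested at week 4, the simulated normalisers-only median is about 12.4 weeks when 66% normalise by week 12 and 12.7 when 30% do (30% is assumed), against true medians of 7.7 and 23.3. A reader might take this as the error built into the plan's own test windows. The documents do not support that. The windows, such as "4 weeks (permitting a window from 3 to 5 weeks) where data are available, and 12 weeks", belong to the change-from-baseline and week-12 percentage endpoints. The time-to endpoints carry none, and Section 6.5.3 collects every dated result from baseline on. Most of that discrepancy comes from assumed sparse testing: at 66%, Kaplan-Meier in all patients is later still (13.5). At 30% it also gives a finite median before week 16 in 95–100% of runs.

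**The weight is limited.** No hypothesis is tested, the endpoints are secondary and descriptive, week-12 percentages are reported alongside, and the number analysed is stated. These points soften the effect. They do not supply a usable definition for three listed endpoints.

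**Conclusion.** The point stands as a should-fix. The stated method does not suit right-censored times, and no section supplies a censoring rule, estimator or risk set. The mean and SD can cover only normalisers. On the plan's 66%, about 34 of 100 patients could fall outside the Hb summary, subject to the qualifications in step 2.

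The direction holds without assumptions about the curve: on the same test dates the reported time is shortened or unchanged. The size does not. At 66% and a constant rate, the median is 0 to about 3 weeks shorter, and the upper end (4.5 against 7.7 weeks) needs frequent testing that the plan does not schedule. Other shapes or lower response can give more. No response rate is given for ferritin or transferrin saturation, so no size is claimed for them.

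The primary endpoint and Table 2 are unaffected.

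**What to change.** Add to Section 9, for each time-to endpoint:

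- **Risk set:** all patients below that parameter's cut-off at baseline.
- **Event:** the first value in the normalised range given in the list of definitions.
- **Censoring:** patients not normalised are censored at their last test of that parameter in the observation period.
- **Estimate:** the cumulative percentage normalised with 95% intervals, and the median if reached, in place of the mean or median among normalisers.
- **Visit-driven dates:** because tests occur only at routine visits, either use an interval-censored estimator or label the Kaplan-Meier result as time to first documented normal test. Either is acceptable; an interval-censored main analysis is not essential.
- **Discontinuation:** state how patients who stop Feraccru® before normalising are handled in the analysis, using the discontinuation date already collected.

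**Cost.** The change needs SAP wording and a little more analysis, with no new data field. Section 6.5.3 names only "Description of IV iron treatment history, to include at least the number of prior infusions", so a date for IV iron after initiation would be needed only if the analysis is to account for it. Intervals will be wider: the interval-censored week-12 percentage is about ±14 points at N = 100 in the sparse-test illustration, against 9.28 for the simple percentage. Some medians will not be reported. A week-4 percentage cannot be estimated by the interval-censored method if few patients are tested around then.
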